#### **Triplicate ECG Recordings – (Screening and Day -1)**

Triplicate recording, including a 10-second rhythm strip, will be obtained approximately 2-4 minutes apart at the initial Screening Visit and at check in to the CRC on Day -1. Each ECG parameter obtained with the 3 assessments will be recorded in the CRF. The average of the triplicate ECG measurements collected at each nominal time point will be used for analysis. The 3 recordings should be immediately assessed as valid recordings and if not valid, they should be repeated in order to obtain a total of 3 valid recordings. Invalid recordings will not be entered in the CRF.

### Single ECG Recordings – (Day 1 through Day 112)

One complete recording, including a 10-second rhythm strip, should be taken at all time points except at the initial Screening Visit and at check in to the CRC on Day -1. It should be immediately assessed as a valid recording and if not valid, it should be repeated. Invalid recordings will not be entered in the CRF.

When a single ECG recording is performed at each time point, the ECG collected predose on Day 1 will serve as the subject's baseline ECG.

To ensure safety of the subjects, a qualified individual at the investigator site will make comparisons to baseline measurements.

If the QTcF interval (calculated online on site) is increased by >45msec from the baseline or an absolute QTcF value is >500msec for any scheduled ECG, then 2 additional ECGs will be collected, approximately 2-4 minutes apart, to confirm the original measurement. If either of the QTcF values from these repeated ECGs remains above the threshold value (>4 msec from the baseline; or is >500msec), then a single ECG must be repeated at least hourly until QTcF values from 2 successive ECGs fall below the threshold value that triggered the repeat measurement.

If QTcF values remain above 500msec (or >45msec from the baseline) for >4 hours (or sooner at the discretion of the investigator) or QTcF intervals get progressively longer, the subject should undergo continuous ECG monitoring. A cardiologist should be consulted if QTcF intervals do not return to <500msec (or to <45msec above the baseline) after 8 hours of monitoring (or sooner at the discretion of the investigator).

If a machine-read QTcF/QTcB value is prolonged, as defined above, repeat measurements may not be necessary if a qualified physician's interpretation determines that the QTcF/QTcB values are in the acceptable range.

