#### **7.2.2.9 Electrocardiogram**

Twelve-lead ECGs will be performed at the times specified in [Table 1](#) and [Table 2](#). Triplicate ECGs will be performed at Screening and Day -1 only. Thereafter, single ECG recordings will be performed at all subsequent timepoints. All ECGs will be performed using the equipment supplied by the CRC.

The following parameters will be recorded on the appropriate CRF page: heart rate, PR, RR, QRS, and QT intervals. The QTcB and QTcF will be derived from the data in the database. The investigator's assessment of the ECG tracing as normal or abnormal must be documented, and if abnormal, his/her determination of whether the abnormality is clinically significant or not will be documented on the tracing and recorded in the CRF.

The subject should be asked to remove all clothing that covers the location of lead placement. The subject should not have exercised or consumed caffeine, alcohol, or nicotine within the timeframe as described in the Restrictions Section [4.3](#). The subject must be resting in the supine position for at least 5 minutes prior to collecting the ECG.

In some cases, it may be appropriate to repeat abnormal ECGs to rule out improper lead placement as contributing to the ECG abnormality. It is important that leads are placed in the same positions each time in order to achieve precise ECG recordings.

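### The QTcF confirmation step reads >4 msec from baseline, while the alert, monitoring and referral steps around it use 45 msec

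*Protocol*

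**What the plan says.** Protocol 7.2.2.9, under Single ECG Recordings, sets out a chain of actions for a prolonged QTcF. Change is measured from the single predose ECG on Day 1.

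- **Alert:** "If the QTcF interval (calculated online on site) is increased by >45msec from the baseline or an absolute QTcF value is >500msec" leads to two further ECGs, about 2 to 4 minutes apart, to confirm the reading.
- **Confirmation:** "If either of the QTcF values from these repeated ECGs remains above the threshold value (>4 msec from the baseline; or is >500msec"; single ECGs must then be repeated at least hourly.
- **Stopping the hourly ECGs:** they continue "until QTcF values from 2 successive ECGs fall below the threshold value that triggered the repeat measurement".
- **Continuous monitoring:** "If QTcF values remain above 500msec (or >45msec from the baseline) for >4 hours", or earlier at the investigator's discretion.
- **Cardiologist referral:** if intervals "do not return to <500msec (or to <45msec above the baseline) after 8 hours of monitoring".

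Three provisions limit how often the chain runs. For validity, each recording is checked at once: "It should be immediately assessed as a valid recording and if not valid, it should be repeated". For lead placement, "it may be appropriate to repeat abnormal ECGs to rule out improper lead placement". For a machine-read prolongation, "repeat measurements may not be necessary if a qualified physician's interpretation determines that the QTcF/QTcB values are in the acceptable range".

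**The concern.** The 500 msec limb is the same at every step. The change-from-baseline limb is 45 msec at every step except confirmation, where the text reads 4. Neither document gives a 4 msec limit anywhere else or a reason for a lower limit at confirmation. The sentence also speaks of a value that remains above the threshold, which can only mean the one already crossed.

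This is a mandatory safety instruction. After an alert, staff who follow the figure would treat a repeat of, say, +10 msec as confirmation of a rise above 45 msec and start hourly ECGs. That repeat is already below the limit at which the hourly ECGs stop. Staff who follow the evident intent would depart from the written number.

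**Working it through.** **1. Limits side by side (Protocol 7.2.2.9)**

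| Step | Change from baseline | Absolute QTcF |
|---|---|---|
| Alert | >45 msec | >500 msec |
| Confirmation | >4 msec | >500 msec |
| Stop hourly ECGs | below the triggering value (45) | below the triggering value (500) |
| Continuous monitoring | >45 msec | >500 msec |
| Cardiologist referral | not back to <45 msec | not back to <500 msec |

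**2. Values that are confirmed and already below the stopping limit**

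Let d be the change from baseline and c the confirmation limit. A repeat is confirmed if d > c or QTcF > 500. It is below the stopping limit if d < 45 and QTcF < 500. Take a baseline of 400 msec (assumed, so that the 500 msec limb does not bind) and whole-msec changes.

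- c = 4: d = 5 to 44 meets both conditions, 40 values.
- c = 45: no value meets both.

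**3. How weak a confirmation +4 msec is**

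With two independent normal repeats of mean change μ and SD σ, the chance that at least one exceeds c is 1 − Φ((c − μ)/σ)². The documents give no QTcF variance, so σ = 8, 10 and 12 msec are assumptions.

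- μ = 0: 52%, 57%, 60% at c = 4; below 0.1% at c = 45.
- μ = 20: 99.9%, 99.7%, 99.2% at c = 4; 0.2%, 1.2%, 3.7% at c = 45.

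**4. How often a needless confirmation would arise by chance**

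Assumptions: no true QTcF change; normal readings with single-ECG SD s; one predose baseline reading b; alert reading a; repeats r1 and r2. The readings a, r1 and r2 are independent of b and have mutual correlation ρ. The 500 msec limb is ignored.

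P(chance alert) = P(a − b > 45) = 1 − Φ(45/(s√2)). For s = 15 this is 1 − Φ(45/21.2) = 0.0169.

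P(needless) = P(a − b > 45 and 4 < max(r1, r2) − b ≤ 45), by numerical integration. Simulation agreed at s = 15 and 20, for example 0.01190 against 0.01191 at s = 15, ρ = 0.

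Number of readings: one ECG on each of Days 2 to 5 plus one at each of the 8 out-patient visits (Protocol 7.1.2.2) gives 4 + 8 = 12 per subject. With 32 subjects (Protocol 9.6) and no dropout, 12 × 32 = 384. The one-per-day count is an assumption. Day 1 postdose readings are left out because the Table 2 ECG row is not readable in the supplied text.

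| s (msec) | P(chance alert) | P(needless), ρ = 0 | × 384 | P(needless), ρ = 0.5 | × 384 |
|---|---|---|---|---|---|
| 8 | 0.000035 | 0.000034 | 0.01 | 0.000028 | 0.01 |
| 10 | 0.000731 | 0.000661 | 0.25 | 0.000507 | 0.19 |
| 12 | 0.004005 | 0.003294 | 1.3 | 0.002398 | 0.9 |
| 15 | 0.016947 | 0.011906 | 4.6 | 0.008365 | 3.2 |
| 20 | 0.055806 | 0.030362 | 11.7 | 0.021323 | 8.2 |

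The ρ = 0.5 columns allow for the alert reading and its repeats being only minutes apart.

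**5. Extra ECGs per needless confirmation**

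In every case counted above, both repeats are at or below +45 msec. If the two repeats may serve as the two successive readings that end the sequence, it ends at once and no ECG is added. If they may not, at least two more follow. The protocol does not say which.

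**The case against.** The strongest objection is that this may not be an error in the plan at all. The text was read from a PDF by a program, and 4 is the only msec figure in this part of the section with a space before the unit, just where a 5 could have dropped out. The SAP introduction also names two protocol administrative change memos (05 Dec 2017 and 26 Jan 2018) that were not supplied and may already correct it. Both points stand as limits on what can be claimed. The spacing clue is weak, though, because spacing before units varies elsewhere in the protocol (300mg and 300 mg), and it fits a typing error in the source just as well.

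A second objection is that the surrounding words correct the figure: a repeat at +10 msec has not remained above a 45 msec threshold. That shows what was intended. It does not remove a wrong number from a mandatory instruction.

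A third objection concerns size, and most of it stands. The error is conservative and acts only after an alert. It may add no ECGs, and an over-read can waive the repeats. The expected counts span about a thousandfold because the SD is assumed. At SD 20 the upper figure rests on about 0.0558 × 384 = 21 chance alerts, which would occur with the correct limit too. SAP 11.4 uses its own ECG criteria, and SAP 18.3 takes the scheduled value, not a repeat, for descriptive statistics.

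**Conclusion.** The concern holds for the text as supplied and is minor. One of the change limits in a five-step safety rule is inconsistent with the rest, and the contradiction disappears when it is set to 45 msec. The practical effect lies between nothing and a modest number of extra ECGs. It is close to nil if single-reading SD is about 10 msec or less. At SD 15 to 20 msec it is about 3 to 12 needless confirmations across the trial, under the normal, no-true-change model and the assumed 384 readings. Detection of prolongation, the monitoring and referral limits, the endpoints and the SAP outputs are unaffected. Confidence is medium, because the supplied text cannot show whether the figure stands in the source document or has since been corrected.

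**What to change.** Check the source page of Protocol 7.2.2.9 and the two administrative change memos. If the figure is there and uncorrected, change the confirmation limit from >4 msec to >45 msec. This is one figure, issued by administrative memo, with no effect on data, endpoints or the SAP.

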### 7.2.3 Pharmacokinetic Procedures

The name and address of the bioanalytical laboratory for this study will be maintained in the investigator's files at the study site and in the Trial Master File at the sponsor.

Actual pharmacokinetic blood sample collection times versus time of dosing will be monitored. The sponsor's expectation is that the investigator will ensure that every effort is made to collect all pharmacokinetic blood samples at the precise protocol scheduled time. Pharmacokinetic blood collection must not deviate from the nominal collection time set forth in the protocol by more than  $\pm 5$  minutes from samples drawn within 4 hours postdose or by more than  $\pm 15$  minutes for samples drawn beyond 4 hours postdose. Samples drawn outside these parameters will be considered a protocol deviation.

#### 7.2.3.1 Pharmacokinetic Sample Collection and Handling Procedures

Pharmacokinetic blood samples will be collected at the time specified in [Table 1](#) and [Table 2](#) to measure plasma concentrations of lanadelumab. A full description of the PK blood collection, handling, storage, and shipping can be found in the provided laboratory manual.

Plasma sample tubes for bioanalysis must be freezer-safe and identified with freezer-safe labels provided by the CRC. The labels will contain the following information:

- Study number
- Subject identifier
- Nominal day
- Nominal time
- Matrix identifier (plasma)
- Split (primary or backup)

#### **7.2.3.2 Shipment of Plasma Pharmacokinetic Samples**

Instructions for shipment of all PK samples (along with the corresponding documentation) can be found in the laboratory manual provided under a separate cover.

Pharmacokinetic samples will be stored nominally at  $-70(\pm 10)^{\circ}\text{C}$  prior to and after analysis at the CRO until further directions are authorized by Shire.

#### **7.2.3.3 Plasma Drug Assay Methodology**

Plasma sample analysis will be performed according to Shire Standard Operating Procedure BC-104 (current version). Under circumstances where this Shire Standard Operating Procedure does not apply, relevant TGA Sciences (the bioanalytical lab) Operating Procedures will be followed.

Plasma concentrations will be measured using the most current validated bioanalytical method. In addition, selected plasma samples may be used to investigate incurred sample reproducibility (full details will be described in the bioanalytical study plan). The presence of other metabolites or artifacts may be monitored or quantified as appropriate. Raw data will be stored in the archive of the designated bioanalytical contract laboratory.

#### **7.2.4 Pharmacodynamic Assessments**

The names and addresses of the bioanalytical laboratories for this study will be maintained in the investigator's files at the site and in the Trial Master File at the sponsor.

Actual PD blood sample collection times versus time of dosing will be monitored. The sponsor's expectation is that the investigator will ensure that every effort is made to collect all PD blood samples at the precise protocol scheduled time. Pharmacodynamic blood collection must not deviate from the nominal collection time set forth in the protocol by more than  $\pm 5$  minutes from samples drawn within 4 hours postdose or by more than  $\pm 15$  minutes for samples drawn at 4 hours post dose and beyond while in the CRC. For PD samples drawn during the out-patient visits refer to [Table 2](#) for time point parameters. Samples drawn outside the parameters set forth in the protocol will be considered a protocol deviation.

#### 7.2.4.1 Pharmacodynamic Sample Collection and Handling Procedures

Pharmacodynamic blood samples will be collected at the time specified in [Table 1](#) and [Table 2](#) to measure plasma concentrations of kallikrein activity and cHMWK. A full description of the PD blood collection, handling, storage and shipping can be found in the provided laboratory manual. Plasma sample tubes for bioanalysis must be freezer-safe and identified with freezer-safe labels provided by the CRC. The labels will contain the following information:

- Study number
- Subject identifier
- Nominal day
- Nominal time
- Matrix identifier (plasma)
- Analyte (kallikrein activity or cHMWK)
- Split (primary or backup)

#### 7.2.4.2 Shipment of Plasma Pharmacodynamic Samples

Instructions for shipment of all PD samples (along with the corresponding documentation) can be found in the laboratory manual provided under a separate cover.

Pharmacodynamic samples will be stored nominally at  $-70(\pm 10)^{\circ}\text{C}$  prior to and after analysis at the CRO until further direction is authorized by Shire.

#### 7.2.4.3 Plasma Pharmacodynamic Assay Methodology

Plasma levels of kallikrein activity and cHMWK will be measured using the most current validated bioanalytical methods. The presence of other metabolites or artifacts may be monitored or quantified as appropriate. Raw data will be stored in the archive of the designated bioanalytical contract laboratory.

#### 7.2.5 Immunogenicity Testing for Anti-Drug Antibodies

The name and address of the bioanalytical laboratory conducting ADA immunogenicity testing for this study will be maintained in the investigator's files at the study site and in the Trial Master File at the sponsor.

Actual ADA blood sample collection times versus time of dosing will be monitored. The sponsor's expectation is that the investigator will ensure that every effort is made to collect all anti-drug blood samples as the precise protocol scheduled time. Anti-drug antibody blood collection will be collected on Day 1 prior to dose (within 60 minutes of dose). See [Table 2](#) for a detailed schedule of time points. A full description of the ADA blood collection, handling, storage and shipping can be found in the provided laboratory manual.

In the event anti-drug antibodies are detected following analysis for a subject, the investigator will be notified by the sponsor. It will be the investigator's responsibility to notify the subject.

## 7.2.6 Volume of Blood to Be Drawn from Each Subject

**Table 3: Volume of Blood to Be Drawn from Each Subject**

Assessment		Sample Volume (mL)	Number of Samples	Total Volume (mL)
Pharmacokinetic samples a		5	14	70
Pharmacodynamic (cHMWK and plasma kallikrein activity) samples		5	14	70
HBsAg, HIV, HCV		8.5	1	8.5
Safety	Biochemistry, FSH and $\beta$ -hCG a,b,c	8.5	12	102
	Hematology	4	12	48
	Coagulation (PT, aPTT, INR)	2.7	11	29.7
Anti-Drug Antibody samples		3	5	15
Total mL				343.2

$\beta$ -hCG=beta-human chorionic gonadotropin; FSH = follicle stimulating hormone; HBsAg=hepatitis B surface antigen; HCV=hepatitis C virus; HIV=human immunodeficiency virus; TSH=thyroid stimulating hormone; T3=triiodothyronine; T4= thyroxine

a If a catheter is used for any blood draw or series of blood draws then the first 1mL is to be discarded. The 1mL discard has been taken into account in the table above and the total blood volume required for this study.

b  $\beta$ -hCG and FSH testing for females only.

c TSH, T3 and T4 will be included in the biochemistry panel, and collected at Screening only.

During this study, it is expected that approximately 343.2mL of blood will be drawn from all subjects, regardless of sex.

Note: The amount of blood to be drawn for each assessment is an estimate. The amount of blood to be drawn may vary according to the instructions provided by the manufacturer or laboratory for an individual assessment; however, the total volume drawn over the course of the study should be approximately 343.2mL. When more than 1 blood assessment is to be done at the time point/period, if they require the same type of tube, the assessments may be combined.

## 8 ADVERSE AND SERIOUS ADVERSE EVENTS ASSESSMENT

### 8.1 Definition of Adverse Events, Period of Observation, Recording of Adverse Events

An AE is any untoward medical occurrence in a clinical investigation subject administered a pharmaceutical product and that does not necessarily have a causal relationship with this treatment. An AE can therefore be any unfavorable and unintended sign (including an abnormal laboratory finding), symptom, or disease temporally associated with the use of a medicinal (investigational) product, whether or not related to the medicinal (investigational) product (ICH Guidance E2A 1995).

All AEs are collected from the time the informed consent is signed until the defined follow-up period stated in Section 7.1.2.3. This includes events occurring during the screening phase of the study, regardless of whether or not investigational product is administered. Where possible, a diagnosis rather than a list of symptoms should be recorded. If a diagnosis has not been made, then each symptom should be listed individually. All AEs should be captured on the appropriate AE pages in the CRF and in source documents. In addition to untoward AEs, unexpected benefits outside the investigational product indication should also be captured on the AE CRF.

All AEs must be followed to closure (the subject's health has returned to his/her baseline status or all variables have returned to normal), regardless of whether the subject is still participating in the study. Closure indicates that an outcome is reached, stabilization achieved (the investigator does not expect any further improvement or worsening of the event), or the event is otherwise explained. When appropriate, medical tests and examinations are performed so that resolution of event(s) can be documented.

### 8.1.1 Severity Categorization

The severity of AEs must be recorded during the course of the event including the start and stop dates for each change in severity. An event that changes in severity should be captured as a new event. Worsening of pre-treatment events, after initiation of investigational product, must be recorded as new AEs (for example, if a subject experiences mild intermittent dyspepsia prior to dosing of investigational product, but the dyspepsia becomes severe and more frequent after first dose of investigational product has been administered, a new AE of severe dyspepsia [with the appropriate date of onset] is recorded on the appropriate CRF).

The medical assessment of severity is determined by using the following definitions:

- Mild:** A type of AE that is usually transient and may require only minimal treatment or therapeutic intervention. The event does not generally interfere with usual activities of daily living.
- Moderate:** A type of AE that is usually alleviated with specific therapeutic intervention. The event interferes with usual activities of daily living, causing discomfort but poses no significant or permanent risk of harm to the research subject.
- Severe:** A type of AE that interrupts usual activities of daily living, or significantly affects clinical status, or may require intensive therapeutic intervention.

### 8.1.2 Relationship Categorization

A physician/investigator must make the assessment of relationship to investigational product for each AE. The investigator should decide whether, in his or her medical judgment, there is a reasonable possibility that the event may have been caused by the investigational product. If there is no valid reason for suggesting a relationship, then the AE should be classified as "not related". Otherwise, if there is any valid reason, even if undetermined or untested, for suspecting a possible cause-and-effect relationship between the investigational product and the occurrence of the AE, then the AE should be considered "related". The causality assessment must be documented in the source document.

The following additional guidance may be helpful:

Term	Relationship Definition
Related	The temporal relationship between the event and the administration of the investigational product is compelling and/or follows a known or suspected response pattern to that product, and the event cannot be explained by the subject's medical condition, other therapies, or accident.
Not Related	The event can be readily explained by other factors such as the subject's underlying medical condition, concomitant therapy, or accident and no plausible temporal or biologic relationship exists between the investigational product and the event.

